## Statistical Analysis Plan

### Objective & Hypotheses

The purpose of the current study is to test the effectiveness of patient-facing, message-based nudges in promoting flu vaccination. Personalized nudges are selected for each patient as most likely to be effective for that individual based on demographic and health characteristics, as determined by a retrospective machine learning algorithm. The algorithm was trained and tested on Geisinger patients who were sent 19 different nudge messages in a 2020 “megastudy” (Milkman et al., 2021). 12 of those nudges are included in the present study.

As detailed below, participants are randomly assigned to one of four arms: the Personalized Nudge arm; the Reserved For You arm, in which they receive the best-performing (on average) nudge from the 2020 megastudy; the Active Control arm, or the Passive Control arm. The primary hypothesis is that Personalized Nudge will outperform each of the other three arms.

### Methods

Patients eligible for the study as of September 9, 2024 were randomized to one of the following arms:

1. Personalized Nudge: nudge predicted to be most effective for the patient on the basis of the machine learning-derived treatment assignment
2. Reserved For You Nudge: nudge found to be on average most effective in the megastudy, including language that a flu vaccine is "reserved" for patients at their upcoming appointment
3. Active Control: a simple message notifying patients they can get a flu shot at their upcoming appointment
4. Passive Control: no message beyond the ambient healthcare system and public health campaigns to increase vaccination

### Power analysis

Based on retrospective data from the 2023 flu season, at least 90,000 patients are estimated to be eligible for enrollment in the current study. The number of patients per arm will vary according to the expected effect sizes for planned analyses. A total of 15,000 patients will be targeted for the passive control arm, with 25,000 patients targeted for each of the other experimental arms. With a baseline primary outcome vaccination rate of 25% expected in the passive control arm, the experimental interventions are expected to increase vaccinations by at least 2 percentage points to 27% on average. By allocating 15,000 patients to passive control and 25,000 to each of the other arms, there will be 80% statistical power to detect, at minimum, a 1.3% increase in vaccination from 25% to 26.3%, with a two-tailed  $p < .05$ . Although personalization is expected to greatly improve nudge effectiveness, differences between active experimental arms tend to be smaller than differences between active and passive arms. Therefore, samples have been

allocated to detect, at minimum, a slightly smaller effect of a 1.1 percentage-point increase from 27.0% to 28.1% across active arms, with 80% power and two-tailed  $p<.05$ .

## Project status

Study recruitment began on September 9, 2024. The anticipated recruitment end date is December 28, 2024. Outcome data have not yet been extracted from electronic health records by the study team.

## Planned Analyses

**Primary Outcome:** Number of patients vaccinated for influenza between enrollment date and target appointment date.

[ *Time Frame: Between the enrollment date and target appointment date (at least 4 days and up to 4 months)* ]

This field experiment will be conducted with Geisinger patients via SMS messages sent prior to their first flu shot-eligible appointment during the study period, referred to as the "target appointment." The key dependent variable is whether patients receive a flu shot at or before their target appointment (as recorded in their electronic health record).

If patients cancel or do not show up for their target appointment after they have been randomized to an arm and then schedule a new appointment during the study period, their new flu-shot eligible appointment becomes the target appointment and the outcome window extends from three days prior to the original appointment through the date of the new target appointment.

Patients who miss their target appointment and do not reschedule within the study period will still be included in the analysis. Their outcome window is from three days prior to the original appointment through the date of the original canceled appointment.

**Primary Question:** Are personalized flu shot messages more effective in increasing flu vaccination rates than the best-performing message in a prior megastudy (Reserved For You), an active control message, and/or no message?

**Secondary Question:** Among the Reserved For You message, the active control message, and no message, how do flu vaccination rates compare? Specifically, does the Reserved For You message lead to higher vaccination rates than both the active and passive control messages, and does the active control message result in higher rates than the passive control?

**Analysis (Confirmatory):** We will test the hypothesis that patients in different arms will exhibit different flu vaccination rates. Specifically, we will compare the following groups:

- Personalized Nudge
- Reserved For You Nudge
- Active Control
- Passive Control

For this analysis, one OLS regression model will be run in the following estimating equation:

$$Y_i = \beta_0 + \beta_1 ReservedForYou_i + \beta_2 ActiveControl_i + \beta_3 PassiveControl_i + \varepsilon_i$$

Where:

- $Y_i$ : Binary outcome variable for patient  $i$  (1 = vaccinated, 0 = unvaccinated)
- $\beta_0$ : Mean vaccination rate in the Personalized Nudge arm (reference category)
- $\beta_1$ : The difference in vaccination rate between the Reserved For You nudge arm and the Personalized Nudge arm
- $\beta_2$ : The difference in vaccination rate between the Active Control nudge arm and the Personalized Nudge arm
- $\beta_3$ : The difference in vaccination rate between the Passive Control nudge arm and the Personalized Nudge arm
- $\varepsilon_i$ : Error term for patient  $i$

Based on this model, we will assess the following pairwise comparisons:

- Personalized Nudge vs. Reserved For You Nudge
- Personalized Nudge vs. Active Control
- Personalized Nudge vs. Passive Control

To estimate the secondary comparisons between study arms (Reserved For You, Active Control, and Passive Control), post hoc pairwise tests will be conducted using the estimated marginal means from the primary OLS model:

- Reserved For You Nudge vs. Active Control
- Reserved For You Nudge vs. Passive Control
- Active Control vs. Passive Control

Recent work suggests that OLS regressions are appropriate in randomized experiments such as this one, using binary outcome variables (Gomila, 2021). We will estimate heteroskedasticity-robust standard errors.

We will not correct for multiple comparisons in the analyses above, as adjustment is not appropriate for individual testing. Each result must be statistically significant to reject its associated individual null hypothesis (Rubin, 2021). Thus, each significant result is an indicator of a specific null hypothesis rejection and has no direct bearing on the success of other hypotheses or the overall study.

EHR flu vaccination data have been finalized and extracted as of this writing but have not yet been analyzed. Insurance claims for flu vaccinations can take up to 90 days to process. To ensure completeness, we will extract the final flu vaccination claims data on April 1, 2025—90 days after the last appointments in the study—plus an additional day to account for potential data refresh delays. In the interim, we will extract an earlier dataset with flu vaccination claims data in the coming weeks for use in preliminary analyses. If there are discrepancies between EHR and claims data regarding vaccine dates, we will use EHR data unless the EHR record is marked as "historic." In such cases, we will use the claims data.

**Heterogeneity Analyses (Exploratory):** We will conduct heterogeneity tests to determine if personalized nudges work better for certain subsets of the population. This will include, but not be limited to, examining factors such as:

- Alignment of the assigned personalized nudge with the received nudge: For participants in the Reserved For You or Active Control arms, we will evaluate whether the effectiveness of the intervention differs based on whether the nudge they received was predicted by the algorithm to be the most effective for them. For example:
  - Aligned: Participants randomized to the Reserved For You or Active Control arm, where the received nudge is the one predicted by the algorithm to be their optimal nudge
  - Misaligned: Participants randomized to the Reserved For You or Active Control arm, where the assigned nudge is not the one predicted by the algorithm to be their optimal nudge
- Feasibility Constraints: Receipt of the optimal nudge versus a different nudge due to feasibility constraints
- Pre-defined sub-groups: Patient groups based on demographic factors such as age and race
- Generalizability: We will assess how the effectiveness of the nudge varies across different clinical contexts, including:
  - Care Setting: The original flu shot megastudy was restricted to primary care target patient appointments. The current study also includes specialty care target appointments. We will compare the relative effectiveness of nudges among patients with target appointments in primary care vs. specialty care to determine whether the impact of nudges depends on the type of healthcare interaction.
  - Patient Population: We will compare the relative effectiveness of nudges among patients who were part of the original training set (i.e., patients in the megastudy) vs. those who are new to the current study to determine whether algorithm-driven predictions maintain validity in previously unseen patients.

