### **Sensitivity analyses and robustness checks**

Statistical analyses will use an intent-to-treat approach, including all patients randomized. However, the analyses described above may also be run with the subset of patients who, according to text message records from Twilio, actually received all their messages as intended and attended their target appointment. This robustness check may exclude patients who were randomized but never sent messages for a variety of reasons (e.g., their phone numbers were inactive, they were on a do-not-contact list the research team did not have access to prior to randomization). This analysis may also exclude patients who received repetitions of the same message, received their texts late, or experienced other message distortions due to technical events outside the study team's control.

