## Other Prespecified Outcomes

Similar exploratory analyses will also be run for the following outcomes, using the same OLS regression models described above.

1. Number of patients with flu shot receipt on or before December 31, 2024

[Time Frame: Up to 4 months after randomization]

2. Number of patients with flu shot receipt between enrollment date and first eligible appointment date

Patients received the flu shot at or before their first eligible appointment date (regardless of whether the patient rescheduled this appointment to a later date within the study period)

[Time Frame: 4 Days]

3. Number of patients with flu diagnosis (encounter diagnosis or flu test)

Patients received a flu diagnosis via encounter diagnosis or flu test between enrollment and April 30, 2025.

[Time Frame: Up to 8 months after randomization]

4. Number of patients with flu-related complications

Patients experienced flu-related complications before as defined by relevant diagnosis, hospitalization, or death, between enrollment and July 31, 2025 as recorded in the electronic health record

[Time Frame: Up to 11 months after randomization]

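### Does an outcome window that depends on rebooking after randomization call for added sensitivity analyses of the primary contrasts?

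*SAP*

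**What the plan says.** The SAP, Planned Analyses, takes as primary outcome a flu shot by the target appointment, with a stated window of 4 days to 4 months. Two rules cover patients who miss or cancel after randomization:

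- If they rebook within the study period, "the outcome window extends from three days prior to the original appointment through the date of the new target appointment".
- If they do not rebook, "Their outcome window is from three days prior to the original appointment through the date of the original canceled appointment".

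The intervention consists of "SMS messages sent prior to their first flu shot-eligible appointment during the study period". Under Methods, Passive Control receives "no message beyond the ambient healthcare system and public health campaigns to increase vaccination".

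Under Sensitivity analyses and robustness checks, the main analysis keeps everyone randomized. The only listed check is optional: "the analyses described above may also be run with the subset of patients who" had, by message records, "actually received all their messages as intended and attended their target appointment".

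Under Other Prespecified Outcomes, the SAP states: "Similar exploratory analyses will also be run for the following outcomes, using the same OLS regression models described above". Outcome 1 on that list is a flu shot by 31 December 2024. Outcome 2 is a flu shot by the first eligible appointment, "regardless of whether the patient rescheduled this appointment to a later date within the study period". Neither depends on rebooking.

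**The concern.** Take two patients who miss the visit and are both vaccinated 20 days later. If one had rebooked for day 30, that shot counts; if the other never rebooked, it does not. Rebooking happens after randomization. The messages refer to the upcoming visit, so they could plausibly change attendance or rebooking relative to no message. If they raise attendance, the messaged arms have fewer extended windows; if they raise rebooking, they have more. Part of a difference from Passive Control could then reflect how long shots were counted and not how many people were vaccinated.

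The listed robustness check does not help. It is optional, and by keeping only attenders it drops patients who missed without rebooking, the group whose window stays short. The two outcomes that avoid the problem are labelled exploratory and are not tied to the primary contrasts. One of the three primary contrasts and two of the three secondary ones involve Passive Control.

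**Working it through.** **1. The plan's own figures.** Inputs from the SAP, Power analysis: 15,000 in Passive Control, 25,000 in each other arm, two-sided 0.05, 80% power. With a two-proportion z-test:

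- 25% vs 26.3%, 15,000 vs 25,000: power 82.1%; the difference detectable with 80% power is 1.26 points, which rounds to the stated 1.3.
- 27.0% vs 28.1%, 25,000 per arm: power 78.6%; detectable difference 1.12 points, which rounds to the stated 1.1.

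These figures reproduce to rounding and are not in dispute.

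**2. How large a shift could rebooking alone cause?** The SAP gives none of the inputs, so these are assumptions. Let m be the share missing the original visit, d the between-arm difference in rebooking among them, and v the chance of a shot after the original date and by the new one. Shift = m × d × v.

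| m | d | v | Shift (points) |
|---|---|---|---|
| 10% | 2 points | 10% | 0.02 |
| 20% | 5 points | 20% | 0.20 |
| 30% | 2 points | 30% | 0.18 |
| 30% | 10 points | 30% | 0.90 |

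In a comparison with Passive Control with no other effect, a shift of 0.20 raises the rejection rate from 5% to 7.3%; a shift of 0.90 raises it to 52.1%. Part of any such shift would be real uptake at rebooked visits.

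**3. What do the planned analyses already show?** Let D = primary outcome minus outcome 2 for each patient. If the new appointment is later than the original, D is 1 for a shot counted only through the moved window and 0 otherwise. OLS is linear in the outcome, so for every pair of arms:

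primary contrast = outcome 2 contrast + D contrast.

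The primary and outcome 2 contrasts are both planned, with the same model, so the point estimate for D is one subtraction.

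**4. What would a formal analysis of D add?** A confidence interval. With p the assumed share of patients with D = 1, the 95% half-width against Passive Control is 1.96 × √[p(1−p)(1/25,000 + 1/15,000)]. Power to detect a true D contrast of 0.20 uses the same standard error.

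| p | Half-width (points) | Power for 0.20 |
|---|---|---|
| 1% | 0.201 | about 50% |
| 2% | 0.283 | about 28% |
| 4% | 0.397 | about 17% |

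For comparison, the primary contrast at 27% vs 25% has half-width 1.96 × √(0.27 × 0.73/25,000 + 0.25 × 0.75/15,000) = 0.885 points. D is estimated 0.885/0.397 = 2.2 to 0.885/0.201 = 4.4 times more tightly, but only because it is assumed rare. In all three rows an estimate of 0.20 would have an interval that includes zero.

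**5. Would a large distortion stay hidden?** In the last row of step 2, at most 30% × 30% = 9% of patients can have D = 1. The half-width is then at most 1.96 × √(0.09 × 0.91 × (1/25,000 + 1/15,000)) = 0.58 points. A gap of 0.90 between the primary and outcome 2 contrasts would be plain from the planned results.

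**The case for a change.** The strongest case for a change is that it costs little and the moment is right. Attendance and rebooking must be coded anyway to build the primary window, the outcome data are stated to be unanalysed, and a prespecified role would make it harder to pass over a divergence as merely exploratory. Intention to treat protects the comparison but does not say whether a difference reflects more vaccination or longer counting. No table of attendance or rebooking by arm is listed in the SAP.

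Much of this is true. The window does depend on rebooking, the optional check cannot reveal it, and the rates by arm would be useful to a reader. But calling outcomes 1 and 2 sensitivity analyses, with no decision rule attached, would alter no estimate, test or claim. An interval for D would be new, but D mixes genuine late uptake with window length, so it cannot isolate the distortion, and it is imprecise for a shift of 0.20 points. Descriptive tables by arm are commonly specified outside an SAP, and the protocol is not at hand.

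**Conclusion.** The observation is correct, but it does not call for a change. Moving the target to the rebooked visit is an explicit choice, applied alike in all arms to everyone randomized, and a message that leads to vaccination at a rebooked visit is plausibly part of the intended effect. Two of the three primary contrasts compare messaged arms with each other, where a difference in rebooking is less likely.

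The direction and size of any distortion cannot be derived from the SAP. On assumed inputs it runs from 0.02 to 0.90 points, with 0.20 as a middle case: a tenth of the expected 2 points and well below the 1.3-point detectable difference. The top of that range would be visible by setting the primary result beside outcome 2, which is already planned with the same model.

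This conclusion rests on outcomes 1 and 2 being run and reported as the SAP commits to, and on rebooked visits falling after the original ones. Analysts may sensibly show the three results together with attendance and rebooking by arm, but that is a matter of presentation.

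### Does the primary outcome window have two different end dates for a patient who rebooks and then misses the rebooked visit?

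*SAP*

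**What the plan says.** The primary outcome in the SAP, Planned Analyses, is "Number of patients vaccinated for influenza between enrollment date and target appointment date". The target appointment starts as the patient's first flu-shot-eligible appointment in the study period (call it A). Two paragraphs then deal with missed appointments.

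- **Rebooking rule.** If A is cancelled or missed after randomization and a new appointment (B) is made within the study period, then "their new flu-shot eligible appointment becomes the target appointment". The end of the window moves to B accordingly, since the SAP adds that the "outcome window extends from three days prior to the original appointment through the date of the new target appointment".
- **No-rebooking rule.** "Patients who miss their target appointment and do not reschedule within the study period will still be included in the analysis". The next sentence reads: "Their outcome window is from three days prior to the original appointment through the date of the original canceled appointment".

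Other Prespecified Outcomes adds two outcomes whose end dates rebooking cannot move. One is a flu shot by December 31, 2024. The other is a flu shot by the first eligible appointment, "regardless of whether the patient rescheduled this appointment to a later date within the study period". Both use the primary model: "Similar exploratory analyses will also be run for the following outcomes, using the same OLS regression models described above".

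**The concern.** The rebooking rule moves the label of target appointment from A to B. The no-rebooking rule is triggered by missing the target appointment, but it ends the window at the original one. A patient who misses A, rebooks B, misses B and books nothing further can therefore be read into both rules, and a shot given after A and up to B would count under one and not under the other.

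Two programmers could then code the only confirmatory outcome differently for the same patients. Because preliminary analyses are planned before the final claims extraction, the choice could in principle be made with results in view. The literal reading also has an awkward feature. A shot obtained elsewhere between A and B would count if B is attended but not if B is skipped, and having had the shot may be the reason for skipping B.

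**Working it through.** **Step 1: apply the rules to each appointment path.**

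- A attended: the window ends at A.
- A missed, nothing rebooked: no-rebooking rule, ends at A.
- A missed, B booked and attended: rebooking rule, ends at B.
- A missed, B booked and missed, C booked: rebooking rule again, ends at C.
- A missed, B booked and missed, nothing further: the rebooking rule and the headline definition end at B. The no-rebooking rule ends at A, but only if it is re-applied with the target moved to B while the original appointment stays at A.

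Only the last path is in question. The two paragraphs divide patients by whether a replacement was booked during the study period. This patient booked one, so the no-rebooking condition is not met. Its reference to a single original cancelled appointment also fits a patient with one missed visit. The natural reading therefore gives B.

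**Step 2: the plan's own figures, as background.** With 15,000 versus 25,000 patients, 25% versus 26.3% and two-sided 0.05, power is 82.1% and the detectable difference at 80% power is 1.26 points, consistent with the stated 1.3. With 25,000 per arm, 27.0% versus 28.1% gives 78.6%, and the detectable difference is 1.12 points, consistent with the stated 1.1. The window question does not affect these figures.

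**Step 3: how many outcomes could change.** The SAP gives no miss or rebooking rates, so every input here is an assumption.

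Share of patients on the disputed path = (share missing A) × (share of those rebooking) × (share of those missing B without rebooking):

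- middle: 0.20 × 0.50 × 0.20 = 0.020, or 1,800 of 90,000
- low: 0.10 × 0.30 × 0.10 = 0.003, or 270
- high: 0.30 × 0.70 × 0.30 = 0.063, or 5,670

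Multiply by the assumed share vaccinated between A and B to get q, the share of outcomes that change:

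- middle: 0.020 × 0.20 = 0.0040, or 360 patients
- low: 0.003 × 0.10 = 0.0003, or 27
- high: 0.063 × 0.30 = 0.0189, or 1,701

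A second set of assumptions (10–30% missing A, 40–60% rebooking, 10–30% missing B, 5–15% vaccinated) gives 18 to 729 changed outcomes.

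**Step 4: effect on a contrast.** Assume q is the same in every arm.

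- Standard error versus passive control: √[0.25 × 0.75 × (1/15,000 + 1/25,000)] = 0.447 points.
- Standard deviation of the difference between codings: √[q(1−q)(1/15,000 + 1/25,000)] = 0.065 points (0.018 to 0.141).
- Between two active arms: √[0.004 × 0.996 × 2/25,000] = 0.056 points, against √[0.27 × 0.73 × 2/25,000] = 0.397. The ratio, about 0.14, is nearly the same as 0.065/0.447 = 0.146.

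**Step 5: how often the codings disagree on p < .05.** One coding's events are a subset of the other's, so the test statistics correlate at √[pₛ(1−p)/(p(1−pₛ))], with p = 0.25 and pₛ = 0.25 − q. That is 0.989 in the middle case (0.999 low, 0.950 high). Simulating pairs of normal test statistics for the contrast with passive control gives:

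- true effect 1.3 points: 3.0% of trials (0.8% to 6.4%)
- true effect 2 points: 0.2% (0.05% to 0.4%)

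If 10% rather than 20% are vaccinated between A and B, q = 0.020 × 0.10 = 0.0020 (180 patients), and disagreement at 1.3 points falls to about 2.1%.

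**The case for a change.** The strongest case for a change is that the SAP itself defines these windows for its only confirmatory outcome, so this is not detail left to a protocol. The rebooking rule expressly moves the label on which the other rule depends, and nothing limits the second rule to patients who never rebook. One sentence would settle it. The SAP also says "EHR flu vaccination data have been finalized and extracted as of this writing but have not yet been analyzed", so the sentence could be added before results are known.

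What stands is that the case is not addressed in so many words, and a literal reader can construct the conflict. That does not amount to a defect in the analysis. Two of the three relevant statements, the headline definition and the rebooking rule, point to B. The third reaches A only by being applied to someone who did rebook. The extra sentence would record the coding an analyst would adopt anyway. A late choice of coding is possible in principle, but it would mean departing from that default for very little movement in any contrast.

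The broader complaint, that the window's length depends on rebooking, which happens after randomization, concerns a stated design choice. Clarifying the disputed path would leave that dependence in place: missing B and booking C would still extend the window. The two outcomes that rebooking cannot move already show the result without the extension, and calling them sensitivity analyses would change no estimate.

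**Conclusion.** No change is needed. This is a small gap in wording with a clear default: a patient who rebooked within the study period falls under the rebooking rule, and the window runs to the rebooked appointment whether or not it was attended. All randomized patients are analyzed, and the comparison between arms is valid under either coding.

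In the middle case, 0.40% of outcomes change (0.03% to 1.89%), and the contrast with passive control moves by about 0.15 of its standard error. Conclusions would rarely differ at the effect of at least 2 points that the SAP expects. The 3.0% figure applies at the minimum detectable effect, where any small recoding matters most. These sizes rest on assumed miss, rebooking and vaccination rates and on equal shares across arms. The middle assumption of 20% vaccinated between two missed visits is generous, since the whole primary rate expected under passive control is 25%. The reading of the rules, on which the conclusion mainly rests, needs none of these assumptions.

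### The confirmatory OLS model is valid but uses none of the pre-randomization data the study holds; a short prespecified covariate list would be a low-priority precision gain of unknown, possibly zero, size

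*SAP*

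**What the plan says.** The SAP, under Planned Analyses, states that "one OLS regression model will be run in the following estimating equation". The equation that follows contains an intercept (the Personalized Nudge mean) and indicators for Reserved For You, Active Control and Passive Control. It has no covariate term. Standard errors are heteroskedasticity-robust. The three secondary contrasts come from the same fit: "post hoc pairwise tests will be conducted using the estimated marginal means from the primary OLS model".

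No adjusted version appears elsewhere. The section on sensitivity analyses and robustness checks varies only the set of patients analysed, and Other Prespecified Outcomes reuses the same models.

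The SAP also shows that baseline data are held for these patients. Under Objective & Hypotheses, nudges are chosen for each patient "based on demographic and health characteristics, as determined by a retrospective machine learning algorithm". The exploratory heterogeneity analyses name "Patient groups based on demographic factors such as age and race", and also compare patients who were in the earlier megastudy with those who were not.

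**The concern.** Baseline data are used to target messages and to form exploratory subgroups, but not to sharpen the confirmatory estimates. Because the SAP prints its full estimating equation, this is a choice the SAP itself makes, not a detail left to a protocol.

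Precision matters most for contrasts between message arms. The Power analysis section says: "Although personalization is expected to greatly improve nudge effectiveness, differences between active experimental arms tend to be smaller than differences between active and passive arms". It sizes those contrasts for a minimum of 1.1 percentage points, from 27.0% to 28.1%. If the true difference is near that floor, a modest reduction in standard error has some value. The expected improvement from personalization also does not bear on "Reserved For You Nudge vs. Active Control", a secondary contrast from the same model that does not involve the Personalized arm.

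**Working it through.** **Inputs from the SAP (Power analysis):** 25,000 patients in each message arm and 15,000 in passive control; 27.0% vs 28.1% between message arms; 25% vs 26.3% (minimum) or 27% (expected) against passive control; 80% power, two-sided 0.05.

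**Input not in the SAP:** R², the share of outcome variance explained by the covariates. I assume a range of 0 to 0.10.

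**Formulas:**
- SE = √[p₁(1−p₁)/n₁ + p₂(1−p₂)/n₂] × √(1−R²)
- Power = Φ(difference/SE − 1.96)
- 95% half-width = 1.96 × SE

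**Step 1: reproduce the stated power (R² = 0).**
- Message arms: SE = √[(0.27×0.73 + 0.281×0.719)/25,000] = 0.3996 points. Power = Φ(1.1/0.3996 − 1.96) = 78.6%. The difference detectable with 80% power is 1.12 points, which rounds to the stated 1.1.
- Against passive control, 25% vs 26.3%: power 82.3%, detectable difference 1.26 points, which rounds to the stated 1.3.

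Both figures agree with the SAP after rounding, and both belong to the unadjusted model.

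**Step 2: message-arm power with adjustment (27.0% in the comparator).**

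| True difference | R² = 0 | R² = 0.05 | R² = 0.10 | Gain over the range |
|---|---|---|---|---|
| 1.1 points | 78.6% | 80.6% | 82.7% | 0 to 4 points |
| 1.25 points | 87.8% | 89.4% | 90.9% | 0 to 3 points |
| 1.5 points | 96.3% | 97.0% | 97.7% | 0 to 1.4 points |
| 2.0 points | 99.9% | 99.9% | 99.9% | essentially none |

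With weak covariates (R² = 0.02), power at 1.1 points is 79.4%, a gain of 0.8 points.

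**Step 3: interval width.** At 1.1 points the half-width is 0.783, 0.763 and 0.743 points for R² of 0, 0.05 and 0.10. The narrowing is 1 − √(1−R²), that is 0%, 2.5% and 5.1%, whatever the true effect.

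**Step 4: contrasts with passive control.** At the expected 25% vs 27%, SE = 0.4515 points and power is already 99.3%. Adjustment matters least here.

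**Step 5: cost if the covariates predict nothing.** With 12 uninformative columns the variance factor is about 25,000/(25,000−12) = 1.0005, an increase of about 0.05%. Power at 1.1 points stays at 78.6%.

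**Check of the formula.** Simulating the planned arm sizes with a binary outcome, 12 centred columns fully interacted with arm, and robust standard errors gave adjusted-to-unadjusted SE ratios of about 1.000, 0.990 and 0.975 at R² of 0, 0.02 and 0.05. This agrees with √(1−R²). It confirms the formula and says nothing about R² in these patients.

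**Which covariates qualify.** Age, race and megastudy membership are known before randomization, as are the health inputs the algorithm used, taken as they stood then. Care setting is different. The SAP defines it by the target appointment, and after a cancellation or missed visit "their new flu-shot eligible appointment becomes the target appointment". As defined, it can change after randomization.

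**The case against.** The strongest objection is that nothing here is wrong. The SAP fixes one closed model, defines every coefficient and specifies robust errors. Randomization makes the unadjusted difference in proportions valid. That stands in full, and it limits the point to an efficiency suggestion. It does not defeat the suggestion, since adjustment keeps the same estimand and the unadjusted result would still be reported.

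Second, the benefit cannot be shown from the SAP. It gives no R², no association between covariates and vaccination, and no prior-season vaccination data. This also stands: the lower end of the gain is zero and must be stated as such.

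Third, 1.1 points is a design floor, not an expected effect, and the SAP expects personalization to do much better. If so, the gain for the Personalized contrasts largely disappears, as the rows at 1.5 and 2.0 points show. That expectation does not cover Reserved For You against Active Control, and the proportional narrowing of intervals applies at any effect size.

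Fourth, changing the confirmatory model now carries a credibility cost. The SAP says that EHR vaccination data are already extracted, though not analysed, and adds: "In the interim, we will extract an earlier dataset with flu vaccination claims data in the coming weeks for use in preliminary analyses". This stands and belongs among the costs.

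A reader might also infer from 78.6% that the trial is underpowered or that the SAP misstates its power. The documents do not support that: the detectable difference of 1.12 points rounds to the stated 1.1.

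**Conclusion.** The point holds as a low-priority efficiency improvement. The confirmatory model is valid and its stated power is sound within rounding. It simply does not use baseline data the study already has.

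Under an assumed R² of 0 to 0.10, adjustment would add 0 to 4 points of power at a 1.1-point difference between message arms (78.6% to at most 82.7%), 0 to 1.4 points at 1.5, and essentially none at 2.0. Intervals would be 0 to 5.1% narrower. The range rests on the planned arm sizes, the SAP's 27.0% comparator rate and an R² that the SAP does not supply.

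Two stronger readings are tempting. One is that omitting covariates biases or invalidates the confirmatory result; under randomization with robust errors it does not. The other is that adjustment would certainly add a few points of power; the SAP offers nothing to exclude a gain near zero.

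**What to change.** Before any arm-level outcome is examined, including the preliminary analyses, amend the SAP as follows.

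- Prespecify a short closed list of covariates fixed at randomization: age, race, megastudy membership, and any health inputs of the algorithm listed by name. Include care setting only as recorded for the original appointment.
- Enter them mean-centred over all randomized patients and interacted with arm, in the same OLS with robust standard errors.
- State a simple rule for missing covariate values.
- Take all six pairwise contrasts from this model and report the present unadjusted model alongside.
- Say which of the two models applies to Other Prespecified Outcomes.

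If arm-level outcomes have already been seen, keep the unadjusted model as confirmatory and label the adjusted one a sensitivity analysis.

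**Cost.** No extra patients are needed. The work is a SAP amendment and four coefficients per covariate column (one main term and three interactions). For illustration, 12 columns give 4 × (12 + 1) = 52 coefficients instead of 4, which is small against 90,000 patients. If the columns are uninformative, the variance cost is about 0.05%. The more serious cost is credibility: with EHR outcomes already extracted, the sponsor must document, with dates, that the list was fixed blind to arm-level outcomes.
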